**8.6 Medical Monitoring**

The study PI, [name], will be responsible for monitoring participant safety during the trial and will be assisted by other study physicians and research coordinators. [name] has extensive experience in clinical trials for alcohol dependence including previous experience with baclofen. Serious adverse events will be reported to the IRB, to the DSMB and to the NIAAA project officer within 24 hours. An annual report documenting all adverse events will be submitted to the NIAAA project officer.

Participants will be contacted by telephone 4 weeks after the final trial visit to ascertain drinking behavior and any physical or psychiatric problems. Individuals with clinically significant problems will be referred for appropriate psychiatric or medical treatment.

No alcohol will be administered to any individual as part of this research project.

### **8.6.1 Data and Safety Monitoring Board**

Data Safety Monitoring Board (DSMB): A DSMB will be established given that the trial will represent the first placebo-controlled trial of high dose baclofen for alcohol dependence. [name], Professor of Psychiatry at UNC-Chapel Hill, will serve as the Chair of the DSMB. [name] is an experienced clinician who has worked with patients with substance use disorders for many years. [name] is also an active clinical researcher and has familiarity with clinical trials. [name], Assistant Professor of Psychiatry and Human Behavior at Brown University, will serve on the DSMB. [name] is a pharmaceutical scientist with experience in clinical trials who has knowledge of the use of baclofen in alcohol dependence. [name], Associate Professor of Statistics at West Chester University and the statistician for the trial, will serve on the DSMB. [name] will have knowledge of how to interpret the dataset and will be familiar with the randomization schedule. [name] will provide unblinded summaries of the trial to the DSMB.

The DSMB will meet once 20 participants have been randomized and then will meet at six month intervals. Meetings will be by teleconference. The DSMB will provide a summary letter to the PI and to the IRB regarding any safety concerns and a recommendation as to whether the study should be stopped or modified for safety reasons. No a priori stopping rules will be established for this Phase II trial.

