### **5.3 Method for Assigning Subjects to Treatment Groups**

Randomization blocks will be prepared by the statistician and provided to the Investigational Drug Services. A minimization random assignment procedure will be used to match subjects on the key moderator (DDD) (< 14 DDD or  $\geq 14$  DDD for men and <10 DDD or  $\geq 10$  DDD for women. Randomization will be linked to sequential study number which subjects receive as they enroll in the study.

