## **5.6 *Blinding of Study Drug (if applicable)***

The study biostatistician, will prepare the randomization schedule and include blocking by high/low DDD ( $\geq 14$  for men and  $\geq 10$  DDD for women) and by gender. The randomization schedule will be given to IDS personnel; investigators will not have access to this information. If a medical or other emergency necessitates breaking the blind, IDS personnel will provide the identity of the medication to the PI or another medical study team member.

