**Primary Efficacy Analysis:** For the Summary measure, we will fit a general linear model on the outcome variable, consisting of main effect for treatment status. Goodness-of-fit, will be analyzed for outliers and influential observations. While these summary measure approaches are simple to implement and commonly used, information concerning the effect of time on the treatment effect is ignored. To understand the impact of time we will also conduct a repeated measures models analysis. From the weekly usage measures we will fit a mixed effects model consisting of main effect for treatment status. This repeated measures approach provides more information about the effect of treatment over time and therefore, more power compared to summary analyses above. We will also include the interaction of time and treatment. The interaction of time and treatment will answer the question as to whether the treatment effect is consistent over the entire treatment period or varies over the weeks. The mixed effects framework offers flexibility for the outcomes, e.g. any usage versus none, or count outcome data, e.g. number of abstinent days (Wolfinger and O'Connell, 1993). Appropriate covariance structure will be determined based on the AIC (Akaike Information Criteria) and BIC (Bayesian Information Criteria). We will evaluate the baclofen effect for changes in CDT using the mixed model approach described above. Within all framework, statistical contrasts will allow us to compare the two levels of BAC to PBO, as well as statistically contrasting the two levels of BAC. The advantage of the statistical contrasts is it allows us to use all available data to estimate the variance (variance-covariance for the repeated measures) of the outcome, while also properly distributing the degrees of freedom for the analytical test to account for the three levels of treatment.

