**Treatment of Missing Data:** With repeated assessments, missing data/attrition is inevitable, but the key thing is that the specified contrasts are not affected due to the presence/absence of data. We will use pattern-mixture models to assess if there is bias due to drop out or missing data (Hedeker and Gibbons, 1997). To address missing data in the survival models, Dupuy and Mesbah(2004) considered jointly modeling time to event data with missing covariate data in order to assess if the missing data is ignorable or non-ignorable. These approaches will be implemented to the fitted cox model. Days in treatment may directly impact the treatment comparison for assessing differences. To control for this potential issue, we will also assess Marginal Structural Cox Regression models (Xiao et al., 2010).

**Adjustment for Covariates:** All modeling approaches allow for the inclusion of covariates. We will include any measures differing at baseline or important potentially confounding measures (i.e. gender, race) in our models to disentangle the intervention effect from these measures

**Specific Aim 2. To test the hypothesis that a history of heavy drinking as assessed by average drinks/drinking day in the 30 days preceding screening predicts baclofen response in alcohol dependence.**

We will include the pre-treatment HDD measure in all models above to examine its predictive merit, as well as its potential moderating impact of the baclofen effect. Moderation effect will be assessed by including the interaction of pre-treatment HDD with the treatment assignment. We will treat pre-

treatment HDD as a continuous measure. We will use mean profile plots based on quartiles of HDD to assess if the continuous measure has a linear, piecewise linear, or curvilinear effect. .

**Specific Aim 3. To test the hypothesis that baclofen, 30 mg/d and 90 mg/d, is superior to placebo in reducing anxiety in alcohol dependence.**

Our analytic procedure is as described in Aim 1 using mixed effects model to account for the repeated measures over time, while contrasting the mean intervention effect as well as assessing the potential moderation effect of pre-treatment HDD.

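### Covariates are to be picked from the data, with no date for fixing the analysis, while the trial statistician sits on a board that receives unblinded summaries

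*Combined protocol and SAP*

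**What the plan says.** **Allocation.** Section 5.3 states: "Randomization blocks will be prepared by the statistician and provided to the Investigational Drug Services". Section 5.6 repeats it: "The study biostatistician, will prepare the randomization schedule", and section 5.4 agrees. Sections 5.4, 5.6 and 8.4 withhold the schedule from the investigators. None of them withholds it from the statistician.

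**DSMB.** Section 8.6.1 says that one of the three members described, "the statistician for the trial, will serve on the DSMB". The next sentences, with names removed, say that a person "will be familiar with the randomization schedule" and "will provide unblinded summaries of the trial to the DSMB". On timing: "The DSMB will meet once 20 participants have been randomized and then will meet at six month intervals".

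**Analysis choices (section 7.2).**
- Covariates: "We will include any measures differing at baseline or important potentially confounding measures", with gender and race given as instances.
- Covariance structure of the mixed model: "Appropriate covariance structure will be determined based on the AIC" and the BIC.
- Transformation: to be judged after looking at the distribution. Arc-sine is described as common in 7.2 and is used to interpret the effect sizes in 7.1.

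No section gives a date for fixing these choices, a separate statistician for the unblinded reports, or a barrier between those reports and the final analysis.

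**The concern.** The plan combines two features. The first is a covariate rule that can be settled only by comparing the arms on accumulated data. The second is a trial statistician who knows the allocation and belongs to the body that sees unblinded summaries during the trial. Together they leave open that covariates are chosen by someone who already knows how the arms compare.

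At stake is the credibility of the primary test. Several adjusted models can each be defended under a rule with no test, threshold or list. If the choice among them can be informed by results by arm, the nominal error rate no longer describes the procedure used. Even if nothing improper happens, the trial could not show afterwards that the choice was made blind.

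**Working it through.** The plan gives no figure for the number of unblinded reports or for the effect of the covariate rule, so there is none to reproduce. The check has three parts.

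**1. Who knows what, and when**

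| Step | Stated | Inferred |
|---|---|---|
| Schedule prepared by the study (bio)statistician | 5.3, 5.4, 5.6 | |
| Trial statistician is a DSMB member | 8.6.1 | |
| The two are the same person | | Natural reading; names removed |
| The statistician provides the unblinded summaries | | Natural reading of 8.6.1; as a member, that person receives them in any case |
| The statistician makes the final model choices | | Not stated: 7.2 is in the first person plural, and the Randomization part of section 6 refers to a data analysis team |
| The summaries contain drinking outcomes | | Not stated; the board's remit is safety |

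**2. Number of meetings**

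Inputs: 120 participants within 48 months (section 4.3); first meeting at 20 randomised, then every six months (8.6.1). Even accrual is an assumption.

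- Rate: 120 / 48 = 2.5 per month.
- First meeting: 20 / 2.5 = month 8.
- Later meetings: months 14, 20, 26, 32, 38 and 44.
- Total within 48 months: 7. The next falls at month 50.

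**3. How much room each open choice leaves**

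The documents give neither the number nor the strength of the candidate covariates, so this is an illustration and not an estimate. A simulation with no treatment effect used 40 per arm, a proportion of 84 days as outcome, the pooled baclofen versus placebo contrast in a general linear model, a two-sided 0.05 test and 3,000 runs per scenario. It assumed 2 to 4 candidate covariates that together explain 10% to 50% of latent outcome variance. The smallest p-value among the permitted models was always taken, which is the worst case.

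| Procedure | Type I error |
|---|---|
| Model fixed in advance (arc-sine, no covariates) | 4.7% to 5.5% |
| Free choice of raw or arc-sine only | 5.2% to 6.1% |
| Free choice of covariate set only | 7.1% to 16.4% |
| Both | 7.8% to 18.0% |

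The Monte Carlo standard error near 5% is sqrt(0.05 × 0.95 / 3000) = 0.4 percentage points, so the transformation alone adds little. The covariate set carries most of the freedom. The covariance structure was not simulated. It applies only to the mixed model and is governed by a fit criterion, although 7.2 gives no candidate list and no rule for when AIC and BIC disagree.

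**The case against.** The strongest objection is that two separate matters are being joined. Whether measures differ at baseline cannot be judged without arm labels or codes, so the covariate rule would be open whoever applied it and whoever sat on the board. That is right, and it is why the remedy is aimed at the rule. Board membership adds that a person who knows the allocation may also have seen summaries by arm before the rule is applied.

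Four stronger readings are tempting but not supported:

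- *The analyst will see efficacy by arm and choose accordingly.* Sections 8.5 and 8.6.1 confine the board's recommendations to safety, section 7 plans no interim efficacy analysis, and no section names the person who chooses the models.
- *The whole model is open.* Section 7.2 already sets a general linear model on the summary measure with a treatment effect and contrasts. Arc-sine is named in 7.2 and assumed in 7.1. AIC/BIC is at least a rule.
- *There are eight unblinded looks, from 48 / 6.* This ignores the wait for 20 randomisations. Even accrual gives seven within 48 months.
- *Removing the statistician from the board would cure the problem.* A statistician who only presents closed reports still sees them. Section 8.6.1 does not mention voting, and two of the three listed members would be left to make recommendations, neither of them described as a statistician.

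**Conclusion.** The point holds in limited form. The covariate rule in 7.2 is data-driven, has no closed list and no date by which it is settled. The plan also allows the person most likely to apply it to know the allocation and to see unblinded summaries about seven times within 48 months. Covariate choice *could* therefore be made with knowledge of the arms. The documents do not show that it will be.

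The size of any bias cannot be computed from the documents. The simulated 7.1% to 16.4% for covariate choice is a ceiling under assumed covariates and deliberate selection. It should not be quoted as the trial's error rate.

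The conclusion rests on two inferences: that the study biostatistician and the statistician for the trial are one person, and that this person takes part in the model choices. If either fails, the board-membership part weakens, but the case for a fixed covariate list remains. This is a worthwhile low-cost improvement, not a flaw that invalidates the design.

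**What to change.** Before the first DSMB meeting, sign and date an analysis specification that does the following:

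1. Replaces the baseline-difference rule in 7.2 with a fixed list for the primary model: the drinks-per-drinking-day randomisation stratum; gender, which 5.6 names as a blocking factor and 7.2 as a covariate; and the baseline value of the outcome from the pretreatment TLFB in section 6. Race may stay if it is named in advance.
2. Fixes the arc-sine transformation already assumed in 7.1.
3. Lists the candidate covariance structures for the mixed model and states which criterion decides if AIC and BIC disagree.

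Optionally, add a sentence to 8.6.1 saying that the trial statistician presents closed reports but takes no part in the board's recommendations. This is secondary: it does not prevent access to unblinded data, and it leaves two of the three listed members to make recommendations.

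The cost is one dated document and, if the option is taken, one sentence, with no extra staff. The downside is less freedom to adapt the model later. A departure would still be possible as a labelled sensitivity analysis.

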## **9 Data Handling and Record Keeping**

### **9.1 Confidentiality**

Information about study subjects will be kept confidential and managed according to the requirements of the Health Insurance Portability and Accountability Act of 1996 (HIPAA). Those regulations require a signed subject authorization informing the subject of the following:

- What protected health information (PHI) will be collected from subjects in this study
- Who will have access to that information and why
- Who will use or disclose that information
- The rights of a research subject to revoke their authorization for use of their PHI.

In the event that a subject revokes authorization to collect or use PHI, the investigator, by regulation, retains the ability to use all information collected prior to the revocation of subject authorization. For subjects that have revoked authorization to collect or use PHI, attempts should be made to obtain permission to collect at least vital status (i.e. that the subject is alive) at the end of their scheduled study period.

### **9.2 Source Documents**

Source data is all information, original records of clinical findings, observations, or other activities in a clinical trial necessary for the reconstruction and evaluation of the trial. Source data are contained in source documents. Examples of these original documents, and data records include: hospital records, clinical and office charts, laboratory notes, memoranda, subjects' diaries or evaluation checklists, pharmacy dispensing records, recorded data from automated instruments, copies or

transcriptions certified after verification as being accurate and complete, microfiches, photographic negatives, microfilm or magnetic media, x-rays, subject files, and records kept at the pharmacy, at the laboratories, and at medico-technical departments involved in the clinical trial.

### **9.3 Data Collection**

Subjects will provide information on alcohol use patterns and symptoms. Mental health symptoms, physical symptoms and general demographic data will be obtained via open-ended interviews and structured questionnaires. Blood and urine samples will be gathered. All data will be entered into case-report forms and then into a secure electronic data base. Subjects will not be identified by name or unique identifying information in the case-report forms or in the electronic data base. A linkage file will be maintained using a code and this will be kept in a secure file cabinet and secure office. The linkage file will only be available to the PI, Co-PIs, and research coordinators.

The Database will be configured in Microsoft Access. Discrepancies will be examined and additional data checks completed as indicated. A closed and password-protected data entry system will be used and only certified study personnel will be able to enter or edit data. Data and user stamping are used to create an audit trail. Range checks, review screens, and error trapping routines are built into the system as quality control procedures. Hardcopy data summaries will be available to the investigators for data analyses. As a final check on data integrity, the investigators and study coordinator will check these outputs against the raw data and resolve any discrepancies. A back up of all archival data will be saved on DVD on a monthly basis.

### **9.4 Records Retention**

It is the investigator's responsibility to retain study essential documents for at least 2 years after the last approval of a marketing application in their country and until there are no pending or contemplated marketing applications in their country or at least 2 years have elapsed since the formal discontinuation of clinical development of the investigational product.

## **10 Study Monitoring, Auditing, and Inspecting**

### **10.1 Study Monitoring Plan**

The investigator will allocate adequate time for such monitoring activities. The Investigator will also ensure that the monitor or other compliance or quality assurance reviewer is given access to all the above noted study-related documents and study related facilities (e.g. pharmacy, diagnostic laboratory, etc.), and has adequate space to conduct the monitoring visit.

We will follow our standard protocol for monitoring of clinical trials. First, subjects are screened to exclude those who might have an increased risk associated with study participation, e.g. renal failure, diabetes mellitus, pregnancy. Pregnancy will be initially screened using a blood test with increased sensitivity compared to urine tests. Second, subjects are monitored on a regular basis with visits at post-randomization weeks 1, 2, 3, 4, 6, 8, 10, 12, 14 and 16. At these visits vital signs are taken and subjects are asked about any side-effects or problems that they are having. At weeks 4, 8, 12 and at termination a liver profile and creatinine level are examined. Participants with elevated creatinine or AST/ALT levels  $> 5X$  ULN or a bilirubin  $> 1.5$  ULN will have their medication tapered and stopped and will be monitored by study physicians. In these instances another liver profile and creatinine will be drawn within 2-4 weeks.

Participants will be contacted by telephone 4 weeks after the final trial visit to ascertain drinking behavior and any physical or psychiatric problems. Individuals with clinically significant problems will be referred for appropriate psychiatric or medical treatment.

## **10.2 Auditing and Inspecting**

The investigator will permit study-related monitoring, audits, and inspections by the IRB, government regulatory bodies, and University compliance and quality assurance groups of all study related documents (e.g. source documents, regulatory documents, data collection instruments, study data etc.). The investigator will ensure the capability for inspections of applicable study-related facilities (e.g. pharmacy, diagnostic laboratory, etc.).

Participation as an investigator in this study implies acceptance of potential inspection by government regulatory authorities and applicable University compliance and quality assurance offices.

## **11 Ethical Considerations**

This study is to be conducted according to US and international standards of Good Clinical Practice (FDA Title 21 part 312 and International Conference on Harmonization guidelines), applicable government regulations and Institutional research policies and procedures.

This protocol and any amendments will be submitted to a properly constituted independent Ethics Committee (EC) or Institutional Review Board (IRB), in agreement with local legal prescriptions, for formal approval of the study conduct. The decision of the EC/IRB concerning the conduct of the study will be made in writing to the investigator and a copy of this decision will be provided to the sponsor before commencement of this study. The investigator should provide a list of EC/IRB members and their affiliate to the sponsor.

All subjects for this study will be provided a consent form describing this study and providing sufficient information for subjects to make an informed decision about their participation in this study. This consent form will be submitted with the protocol for review and approval by the EC/IRB for the study. The formal consent of a subject, using the EC/IRB-approved consent form, must be obtained before that subject undergoes any study procedure. The consent form must be signed by the subject or legally acceptable surrogate, and the investigator-designated research professional obtaining the consent.

## **12 Study Finances**

### **12.1 Funding Source**

This study is funded, in part, by a grant from the NIH.

### **12.2 Conflict of Interest**

Any investigator who has a conflict of interest with this study (patent ownership, royalties, or financial gain greater than the minimum allowable by their institution, etc.) must have the conflict reviewed by a properly constituted Conflict of Interest Committee with a Committee-sanctioned conflict management plan that has been reviewed and approved by the study sponsor prior to participation in this study. All University investigators and staff will follow the University's conflict of interest policy.

